Tolerance of Uncertainty. The Intolerance of Uncertainty Scale (IUS) will be used to measure emotional, cognitive, and behavioral reactions to uncertainty situations. Participants indicate how characteristic 27 items are of them on a scale ranging from 1 (not at all characteristic of me) to 5 (entirely characteristic of me), with higher scores indicating greater intolerance of uncertainty. The IUS has demonstrated evidence of excellent reliability and validity in cancer samples.

Quality of Life. The Functional Assessment of Cancer Therapy - Lung Cancer version (FACT-L) will be used to assess quality of life across 5 domains (physical, emotional, social, functional, lung cancer-specific concerns).

Illness Acceptance. The Peace, Equanimity, and Acceptance in the Cancer Experience (PEACE) scale - Peaceful Acceptance of Illness sub scale will be used to assess illness acceptance.

DBT Skill Use. The DBT Ways of Coping Checklist (DBT-WCCL) – DBT Skills Subscale (DSS) will be used to assess patient-reported frequency of skill use to manage difficult situations. To avoid response bias, DBT language and the names of skills are avoided in the scale and general descriptions are used. Items are rated on a 0-3 scale, indicating if the coping strategy was never, rarely, sometimes, or regularly used in the past month when faced with a stressor. Items that are not aligned with skills that are included in DBT-MLC following study adaptation procedures (Phase 1) will be removed. The DSS has demonstrated evidence of reliability and validity, including criterion validity to accurately measure DBT skill use, in studies of patients undergoing DBT treatment.

e. Qualitative Exit Interviews. We will conduct qualitative exit interviews with pilot participants to inform DBT-MLC intervention refinement. All participants will be offered the opportunity to participate in a qualitative exit interview after completing the post-intervention assessment. Qualitative exit interviews will follow similar procedures to the stakeholder interviews.

Risk/Benefit Assessment

• Include a thorough description of how risks and discomforts will be minimized (per 45 CFR 46.111(a) (1 and 2)). Consider physical, psychological, legal, economic and social risks as applicable. If vulnerable populations are to be included (such as children, pregnant individuals, imprisoned persons or cognitively impaired adults), what special precautions will be used to minimize risks to these subjects? Also identify what available alternatives the person has if he/she chooses not to participate in the study. Describe the possible benefits to the subject. What is the importance of the knowledge expected to result from the research?

Risks

Participation poses minimal risk to participants. No adverse events are anticipated. Participation in all phases of the study is voluntary and participants can withdraw at any time. The risks associated with all phases of this study are minimal and rare. First, participation in either a focus group, interview, or a psychological treatment intervention is associated with few negative side effects. The focus groups, intervention sessions, assessments and exit interviews will cover topics including cancer diagnosis and treatments, symptoms of psychological distress (i.e., depression and anxiety), physical symptom burden (i. e., fatigue, dyspnea, pain), as well as emotion regulation, tolerance of uncertainty, and DBT skill use. Although some participants may find certain questions or topics to be upsetting, heightened awareness of existing psychosocial and practical needs may be the first step in resolving these concerns. All of these topics may involve participants providing sensitive and personal information. Participants may feel embarrassed or uncomfortable with disclosing this information. All efforts will be made to remain sensitive to participant's needs, HIPAA requirements, and confidentiality procedures.

Participants will be fully informed about the study during the informed consent process and instructed to decline to answer any question or to discuss any issues they find troubling. If a participant reports significant distress during study participation, [name] (licensed clinical psychologists) will be consulted. Participants who report suicidality will be managed following the Suicide Prevention Plan included in "Other Study Documents". If the participant requires additional treatment, appropriate referrals will be made. The study team has extensive experience conducting psychosocial intervention trials with cancer patients and have not encountered significant psychological distress caused by study participation. Moreover, cancer patients and their family caregivers often report benefits from participating in psychosocial research. Thus, the risk of psychological distress is modest and the safeguards should be adequate.

In a group setting, such as in a focus group or treatment group, there is risk of disclosure of personal information by another participant. Groups will be instructed to maintain participants' confidentiality at the onset of the group, and participants will be asked not to share what goes on during the group. Additional efforts will be employed to maintain confidentiality. Two password-protected databases will be used to ensure confidentiality of participant information and data by keeping identifying information separate from research records. The first database, used for tracking and recruitment, will house the contact information of individuals who may be eligible for the study as well as participants who have agreed and those who have declined to participate. No medically sensitive information or outcome data will be stored in this database, and all identifiable data of non-participants (e.g., names) will be deleted. All study data will be stored in a separate, password-protected database. Participants will be assigned separate subject numbers, and data will be stored in the database under the subject number.

The IRB-approved study team members will use a Duke encrypted laptop for data collection and recording of stakeholder interviews and study sessions. After focus groups and sessions are completed, audio recordings will be saved to the Duke University Medical Center psychiatry server and deleted from the laptop. All audio recordings will be deleted at the end of the study. Deidentified transcripts of focus groups and exit interviews will be stored in separate password protected files. Both databases and transcripts will be kept on the Duke University Medical Center psychiatry server housed behind the DUMC firewall. If necessary, paper copies of assessment packets will be filed by subject number and housed in a locked cabinet in a locked office in the PPTRP offices. Only [name], her sponsor ([name]), and mentors affiliated with the project will have access to the research records. To ensure that there are no changes in potential risk during the study, and that confidentiality is maintained, a Data and Safety Monitoring Plan (see below) will be implemented.

Study tablets may be used for data collection (through REDCap). If necessary and appropriate, patient participants in Phase II of the study may be provided with a device (e.g., tablet computer) to participate in the pilot intervention program. A data plan will be provided if necessary. These will be set with restrictions. Specifically, the following steps will be taken: 1) Duke Mobile Device Manager (MDM) will be installed on all devices; 2) Study staff will keep the operating system on the most current version (Settings>General>Software Update); 3) We will enable encryption on the device (Settings>Passcode) and verify that data protection is enabled, set "require passcode" to immediately, and enable erase data to "automatically erase the device" after 10 failed passcode attempts; 4) We will set Auto-Lock. 4) Study

staff will use Restrictions to restrict any unnecessary access including changing account settings (Settings>General>Restrictions); 5) We will reset devices between use for different participants (Settings>General>Reset>Erase All Content and Settings); and 6) At end of device life, we will send the device to Duke Procurement Surplus & Salvage for secure destruction.

Alternative options to participating in the current study include choosing not to participate. Participants may choose to seek alternative psychosocial treatment through the Cancer Patient Support Program at DCI, or in another clinic at Duke or in the community. Benefits of receiving psychological services outside of the study may also include reduced psychological distress. However, the proposed DBT-MLC is specifically designed to be relevant and acceptable to patients with metastatic lung cancer, and therefore may represent a better fit for the needs of these patients compared to traditional therapeutic approaches.

The risks to non-patient stakeholders are minimal and primarily include psychological distress and breach of confidentiality. Non-patient stakeholders will be asked to evaluate the DBT-MLC protocol by reviewing session handouts outlining educational content and dialectical behavioral therapy strategies to address emotional (e.g., anxiety, depression) and behavioral symptoms (e.g., pain, fatigue, dyspnea). Providers will also be asked about preferences for intervention structure (i.e., individual delivery, session length etc.) and delivery modality (i.e., in-person, telephone, or videoconference), and to describe potential barriers to attendance. These questions are unlikely to cause psychological distress, however, providers will be reminded that they can decline to answer any question or to discuss any issues they find troubling. Breach of confidentiality is another possible risk. This is clearly stated in the consent form. All efforts will be made to maintain confidentiality. Participants' data and research records will be carefully stored. All study personnel will be required to complete courses and ongoing training in protecting participant confidentiality.

Benefits

There are several potential benefits of study participation. All participants will have the opportunity to discuss their emotional and physical symptoms with an interested interviewer, and potentially with others facing a similar situation. Providers and patients who participate in interviews and/or focus groups may learn skills that can help to reduce patient distress and improve emotional and behavioral symptom management. Participants in the pilot study will receive an evidence-based treatment aimed at reducing psychological distress at no cost. The benefits to society could include increased knowledge of the emotional and physical symptom burden of patients with metastatic lung cancer, as well as information about whether participating in an adapted DBT-MLC protocol can reduce psychological distress (i.e., depression, anxiety) improve physical symptoms (fatigue, dyspnea, pain), as well as improve emotion regulation and intolerance of uncertainty.

Costs to the Subject

• Describe and justify any costs that the subject will incur as a result of participation; ordinarily, subjects should not be expected to pay for research without receiving direct benefit.

There is no cost to the study subjects.

Data Analysis & Statistical Considerations

Describe endpoints and power calculations. Provide a detailed description of how study data will be
analyzed, including statistical methods used, and how ineligible subjects will be handled and which
subjects will be included for analysis. Include planned sample size justification. Provide estimated time
to target accrual and accrual rate. Describe interim analysis including plans to stop accrual during
monitoring. Phase I studies, include dose escalation schema and criteria for dose escalation with
definition of MTD and DLT.

Data management and attrition. Participant identifying information will be stored in a secure study database. It will not be stored with questionnaire data to protect patient confidentiality. We anticipate approximately 26% attrition from baseline to immediately post-intervention based on previous supportive care interventions in people with cancer. ⁹⁰ Therefore, we will recruit approximately 38 participants to obtain full data from 30 participants. Reasons for withdrawal will be collected when possible. Data will be checked on an ongoing basis for completeness. If data are determined to be missing systematically, we will consider statistical approaches to manage data missingness (i.e., data imputation methods). [name] will work with statistical experts to determine the most appropriate methods for handling missing data. **ii.**

Statistical Power. Phase 1 will include 4-6 focus groups of approximately 5 patient stakeholders each (N=20), and individual interviews with thoracic oncology providers (N=6) and palliative care, survivorship and behavioral symptom management experts (N=6). Assuming the same potential rate of attrition for focus groups due to scheduling conflicts, illness, etc., we will recruit up to 26 participants to get focus group data from 20 participants (assuming 26% attrition). For Phase 2, we will recruit up to 38 participants to get complete data on approximately 30 participants (assuming 26% attrition). These numbers were calculated based off of relevant literature and work that has been previously successfully completed in this setting. 64,90 Literature suggests that 2-3 focus groups are necessary to reveal 80% of qualitative themes.

Analytic Plan.

Aim 1: Adapt Intervention. In-depth interviews and focus groups will be transcribed verbatim using QSR NVivo software. Data analyses will be based on a grounded theory approach, which has been used in the development of other psychosocial interventions for patients with cancer. ⁹² [name] will complete several workshops on analyzing qualitative data (see Training Plan). Additionally, the PI and members of the mentoring team have experience with qualitative data analyses. [name] is a member of the Cancer Control and Population Sciences Program at DUMC, which has a shared resource of qualitative analytic experts. Experts will be consulted as necessary to ensure appropriate handling and conducting of qualitative analyses.

iv. Aim 2: Test and Refine Intervention. Descriptive statistics (frequencies, mean, median, standard deviation) will be used to examine feasibility (i.e., \geq 80% of sessions completed, attrition \leq 25%) and acceptability (i.e., \geq 80% participants report satisfaction on CSQ). Paired sample t-tests will be run to quantify the degree of change over time for the primary and secondary intervention outcomes. Effect sizes will be computed using Cohen's d. Unconditional latent growth models will be used to assess main time effects across baseline, immediately post-treatment and 1 month post-treatment. Time will be coded as the number of weeks since the baseline assessment. Control variables and their interactions with time will be included in conditional models. Analyses will be conducted using an intent-to-treat approach to include all available data (N=up to 38). Exit interviews will be coded and analyzed using methods similar to those described under Aim 1. Themes and feedback that are uncovered through exit interviews will be used to inform intervention refinement.

Data & Safety Monitoring

• Summarize safety concerns, and describe the methods to monitor research subjects and their data to ensure their safety, including who will monitor the data, and the frequency of such monitoring. If a data monitoring committee will be used, describe its operation, including stopping rules and frequency of review, and if it is independent of the sponsor (per 45 CFR 46.111(a) (6)).

The proposed study carries minimal risk. The protocol does not use an investigational drug, procedure, or device. Data obtained from participants will include information from medical chart review, stakeholder interviews and focus groups, and self-report inventories. The study team considers the management of participant information and data as a key priority. Best practices for confidentiality and data management will be observed. Two password protected databases will be used for this study to ensure confidentiality.

First, a tracking database will be used for recruitment and follow-up. This data will house information related to tracking the participants in the study, such as phone numbers and addresses. No medically sensitive or outcome data will be stored in this database. This database will also track nonparticipants (i. e., those who have declined participation) only to the barest minimum to ensure that they are not contacted again about participation. At the end of the study, all identifiable data of non-participants such as their names will be deleted. Tracking data on participants will be retained for the usual required period. Second, all study data will be stored in a separate password protected database without any personal identifiers. Data in this database will be derived from patients' direct input into the electronic patient reported outcomes system, Redcap, which is an online survey system; data entered into this system is stored on a secure server housed behind the DUMC firewall. Only a unique study identification number will link the electronic data to the study data file. The tracking data and study data will be stored in a file on a secure DUMC psychiatry server which can only be accessed by necessary members of the research team. Access to the Duke network requires a password protected, 128-bit encrypted virtual private network connection provided by Cisco systems. If necessary, all paper research records (e.g., completed paper questionnaires) will be kept in a locked file cabinet. Only [name] (PI), [name] (F32-awardee and study coordinator), and study members with approved affiliation to the project will have access to the research records. Additionally, individuals participating in focus groups will be instructed to maintain participants' confidentiality at the onset of the group. Participants will be asked not to talk about other participants' comments outside of the group.

All participants in the study will continue their medical care during the course of the study and will be informed that choosing to participate in the study will in no way impact the treatment they receive at the DCI and DUMC. All participants will continue to be monitored by their physicians at the DCI throughout the course of the study. If a health concern is identified during contact with study staff, the patients' treating oncologist will be contacted, and appropriate referrals for medical treatment will be provided to patients. [name] (PI), [name] (F32-awardee and study coordinator) will continuously monitor and tabulate adverse events. An adverse event is any untoward medical event occurring during the clinical evaluation, which is causally related to the study protocol. A serious adverse event is defined as any event which results in death, is immediately life threatening, results in persistent or significant disability/incapacity, results in patient hospitalization, or is serious for any other reason representing significant hazard. For each event, the investigator will provide the onset, duration, intensity, treatment required, outcome, and action taken. Given the study population (i.e., patients with metastatic lung cancer), it is possible that some participants will be hospitalized and/or die while enrolled. Adverse events due to advancement of lung cancer will not be reported, as these are unrelated to participation in this supportive behavioral intervention. If an unexpected frequency of Grade III or IV events occur, depending on their nature, action appropriate to the nature and frequency of these adverse events will be taken. This may require a protocol amendment, dose de-escalation, or potentially closure of the study. [name] (PI), [name] (F32awardee and study coordinator) will also continuously monitor the conduct, data, and safety of this study to ensure that:

- Risk/benefit ratio is not altered to the detriment of the subjects;
- Appropriate internal monitoring of AEs and outcomes is done;
- Over-accrual does not occur;
- Under-accrual is addressed with appropriate amendments or actions;
- Data are being appropriately collected in a reasonably timely manner.

All interactions with study participants will be conducted under the direction of licensed clinical psychologists (Drs. [name], [name], and [name]). Audio and video recordings of patient interactions (focus groups, treatment sessions) will also be obtained and reviewed with Drs. [name], [name], and [name] to ensure that [name] is providing effective and ethical treatment. [name] has experience working with distressed patients with chronic disease in clinical research contexts. [name] will be carefully trained to monitor participants' psychological status and report to Drs. [name] [name], and [name] if a participant shows signs of experiencing high levels of physical and emotional distress that need to be addressed outside of the context of this study. If this is determined to be the case, [name] will work directly with Drs. [name], [name], and [name] and make recommendations for the participant to move forward in a way that is in the best interest of the participant. Drs. [name], [name] and [name] are practicing licensed clinical psychologists and supervise psychology trainees (i.e., advanced graduate students, clinical psychology interns). [name] is integrated into the psychosocial care program at the DCI (i.e., Duke Cancer Patient Support Program) and the community. [name] has experience referring cancer patients and other individuals who are highly distressed to appropriate psychosocial or psychiatric care. She will use the same resources when making referrals for extremely distressed participants in this study. Likewise, [name] is a provider on the Duke Palliative Care service within the Duke Department of Psychiatry and Behavioral Sciences, where she provides psychological treatment for chronically ill patients. [name] is an expert in the treatment of highly distressed, difficult-to-treat cases where there are multiple comorbidities combining psychological and medical problems using DBT.

Likewise, [name] (PI) and [name] (F32-awardee and study coordinator) will appoint two data safety officers. One data safety officer will be a MD within the Duke University Medical Center (DUMC) who is not associated with this study. The appointed MD officer will have experience with clinical research and trials, and will have a thorough understanding of adverse events. The other safety data officer will be a DUMC senior investigator who has expertise in psychological treatment and behavioral symptom management, and will have an annual responsibility to evaluate our current methods of assessment and intervention to identify any problems. All adverse events will be reported to the data safety officers in real time.

This study will also be monitored institutionally by the Duke Cancer Institute (DCI). DCI Protocol Review and Monitoring systems (PRMS) review of this protocol begins with an initial review by the Cancer Protocol Committee (CPC). CPC new protocol review focuses on scientific relevance, study design, adequacy of biostatistical input, protocol prioritization, feasibility of completing the study within a reasonable time frame and risk assessment of the trial. The PI will abide by CPC assessment of the level of risk, which will determine the intensity of subsequent DCI monitoring. CPC also conducts annual scientific progress reviews on protocols that are open to enrollment and focus on protocol prioritization, accrual and scientific progress. These reviews are conducted at the time of IRB annual renewals and documentation of all CPC reviews will be maintained in eIRB/iRIS systems.

A determination for the degree of monitoring conducted by the DCI monitoring team is made at the time of initial CPC approval to commensurate with the type and level of intervention, phase, endpoints, degree of risk, size and complexity of the protocol. A formal, independent monitoring will be conducted by the DCI monitoring team according to the risk level and monitoring plan assigned by the CPC until the study is closed to enrollment or subjects are no longer receiving study drug or other interventions that are more

than minimal risk. Additional monitoring may be prompted by findings from monitoring visits, unexpected frequency of serious and/or unexpected toxicities, or other concerns. Monitoring visits may also be initiated upon request by DUHS and DCI Leadership, CPC, SOC, a sponsor, an investigator, or the IRB. The DCI monitoring team reviews the adequacy of informed consent, enrollment of eligible patients, implementation of protocol-specified procedures and treatment, adequacy of data collection, and appropriateness of adverse event monitoring and reporting. The DCI monitoring team presents final monitoring reports to the DCI Safety Oversight Committee (SOC) highlighting safety concerns and unresolved issues. The SOC, at a convened meeting, assigns an overall rating of satisfactory, marginal, or unsatisfactory to reflect the overall quality of data, regulatory, consent, eligibility, study conduct and AE reporting. Corrective action plans (CAPs) are developed, implemented, and evaluated as indicated. The SOC will notify the sponsor-investigator and DUHS IRB when significant safety concerns are identified. The SOC in concert with DCI monitoring team conducts data and safety monitoring for DUHS sponsor investigator phase I and II, therapeutic interventional oncology studies that do not have an independent DSMB. These reviews occur at a minimum annually and more frequently for the high risk studies. The SOC safety reviews include review of safety data, enrollment status, stopping rules if applicable, accrual, toxicities, reference literature, and interim analyses as provided by the sponsor-investigator. The SOC, at a convened meeting, assigns a rating of satisfactory when adequate accrual with lack of excessive toxicity is present. Privacy, Data Storage & Confidentiality • Complete the Privacy and Confidentiality section of the iRIS submission form.

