Using the information gleaned from stakeholder interviews, will draft an initial protocol (provider treatment manual, patient materials) for the adapted evidence-based treatment, DBT-MLC. Once the initial protocol has been developed, we will consult with experts in DBT to ensure the protocol remains true to the spirit of the original evidence-based intervention. We will also consult with experts in implementation science to evaluate the potential for adoption and integration of DBT-MLC into healthcare. No individual identifiable participant information will be provided in the protocol sent to topical experts. Feedback from topical experts will be integrated into the adapted DBT-MLC treatment protocol and materials. This will produce a final draft of DBT-MLC for pilot testing.

Phase 2 (Months 13 to 36): Test and Refine the Intervention.

Data from stakeholder interviews in Phase I has informed the final intervention structure and delivery characteristics (e.g., group vs individual, treatment dose, session length, acceptability of telehealth) as well as content and materials (e.g., relevance of skills, examples, activities). This has produced the adapted DBT-MLC intervention, "LiveWell", which consists of 8 sessions, approximately 45-60 minutes in length, delivered approximately weekly. Stakeholder insights determined that skills training will be done individually (versus in a small group setting). Given the benefits telehealth offers with regard to access and research demonstrating its acceptability and feasibility with cancer patients, the intervention will be delivered remotely. An overview of proposed session content is provided in the Table below. It is anticipated that participation in the intervention will take approximately 12 weeks overall.

Table. Session Topics, Skill Content, and Homework Assignments

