We will assess the feasibility, acceptability, and pre-to-post intervention improvement in outcome variables using a single-arm pilot study (N=30). Standardized self-report assessment measures will be administered at baseline, immediately post-intervention, and 1 month follow-up. Participants can complete assessments via hard copy or online via RedCap. All participants will be offered participation in an exit interview to inform DBT-MLC refinement. If necessary and appropriate, patient participants in Phase II of the study may be provided with a device (e.g., tablet computer) to participate in the pilot intervention program. A data plan will be provided if necessary. These will be set with restrictions. Participants will return tablet computers following completion of study activities.

Study personnel will be trained in procedures related to delivering DBT-MLC. [name] will attend formal trainings in delivering DBT skills training as part of the fellowship project. She will create a standard operating procedure manual for the delivery of DBT-MLC. Study interventionists will thoroughly review the treatment manual and rehearse intervention delivery by role playing skills training sessions.

• List inclusion/exclusion criteria and how subjects will be identified.

Eligibility criteria for patients. Eligibility criteria for patients were determined in consultation with mentor and thoracic oncologist, [name], MD, and based on previous psychosocial studies in advanced lung cancer.

Eligibility criteria for patients included in Phase I and Phase II include:

- 1) be diagnosed with metastatic (AJCC stage IV) non-small cell lung cancer,
- 2) be undergoing systemic treatment (chemotherapy, targeted therapy, and/or immunotherapy) for lung cancer at DCI.
- 3) score \geq 3 on the National Comprehensive Cancer Network Distress Thermometer for distress over the past week (Range: 0-10),
- 4) be > 18 years of age,
- 5) be able to understand, speak, and read English, and
- 6) be able to provide informed consent.

Exclusion criteria for patients include:

- 1) reported or suspected cognitive impairment subsequently informed by a Montreal Cognitive Assessment (MOCA) of <26;
- 2) presence of untreated serious mental illness (e.g., schizophrenia) indicated by the medical chart, treating oncologist, or other medical provider; or
- 3) expected survival of 4 months or less.

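### No outcome-assessment date is defined for patients who stop or stall in the sessions, so post-baseline data may come mainly from finishers

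*Combined protocol and SAP*

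**What the plan says.** Design & Procedures, Phase 2, sets the schedule: "Standardized self-report assessment measures will be administered at baseline, immediately post-intervention, and 1 month follow-up". The Aim 2 part of the Analytic Plan describes growth models for "main time effects across baseline, immediately post-treatment and 1 month post-treatment", so the last assessment is also counted from the end of treatment.

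The end of treatment is not a fixed time. The Phase 2 text says the intervention "consists of 8 sessions, approximately 45-60 minutes in length, delivered approximately weekly", and then: "It is anticipated that participation in the intervention will take approximately 12 weeks overall".

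On analysis, the Aim 2 plan states: "Paired sample t-tests will be run to quantify the degree of change over time for the primary and secondary intervention outcomes". For the growth models: "Time will be coded as the number of weeks since the baseline assessment". On the analysis set: "Analyses will be conducted using an intent-to-treat approach to include all available data (N=up to 38".

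On losses, the data management paragraph says "We anticipate approximately 26% attrition from baseline to immediately post-intervention", and recruits about 38 patients to have full data on 30. For patients who miss sessions or leave, the plan asks for reasons. It does not mention an outcome assessment for them. The missing-data method is left to be chosen later.

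No section gives an assessment window, a longest time allowed for finishing the sessions, a number of sessions that counts as having reached the post-intervention point, or a due date for someone who never reaches it.

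**The concern.** Coordinators need a date on which to send a packet. For a patient who finishes the eighth session the date is clear. For a patient who stops after session 3, or is in hospital mid-course, the text supplies none. The simplest way to follow it is to send nothing, and the post-baseline data then come mainly from finishers.

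The plan gives reasons to expect that this matters. Data & Safety Monitoring says some participants may be hospitalized or die while enrolled. The Background reports that earlier studies of this therapy in cancer had trouble with attendance and questionnaire completion. It also links fatigue, dyspnea and pain to distress, and names high symptom burden as a barrier to delivering such interventions. Stopping is therefore plausibly related to the outcomes being measured.

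The same trigger governs the Client Satisfaction Questionnaire (CSQ), which is given post-intervention, and the exit interview, which is offered after the post-intervention assessment. The Background makes feasibility, acceptability and positive pre-to-post change the basis for a larger randomized trial. A finishers-only picture would feed directly into that decision.

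**Working it through.** **The plan's own figure.** 30 × (1 + 0.26) = 37.8, which rounds to the stated 38. Dividing instead gives 30 / (1 − 0.26) = 40.5, so 41. That is a separate matter, and this point does not depend on it.

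**How many patients could be affected.** Inputs are 38 recruited and 26% attrition to post-intervention.
- 0.26 × 38 = 9.9 lost, and 38 − 9.9 = 28.1 observed.
- At the plan's 25% feasibility limit, 0.25 × 38 = 9.5 lost.
- The 26% counts loss of data for any reason. Those who die or leave all contact are lost under any schedule. The share lost only because no date was set is not given, so the range is 0 to about 10.

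**When the assessments fall.** One month is 365.25 / 12 / 7 = 4.35 weeks.
- If the sessions run weekly, the last is at about week 7 or 8, and follow-up at about week 7 + 4.35 = 11.3 to 8 + 4.35 = 12.3.
- If the sessions take 12 weeks, follow-up is at 12 + 4.35 = 16.3.
- For a stalled patient no limit is stated.

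**What each analysis does with a patient who has only a baseline score.**
- A paired t-test and its Cohen's d need both scores, so the patient drops out. Neither has a term for the length of the interval.
- The growth models code actual weeks and so can use unequal intervals among patients who were assessed. A patient with only a baseline score adds no observed change.

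**Illustration for the primary outcome (assumed effects).** Suppose 28 finishers change by d_f, and k further patients who could have been reached change by d_s, in units of a common standard deviation. The mean over everyone reached is (28 × d_f + k × d_s) / (28 + k).

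| d_f | d_s | k | Mean over all reached |
|---|---|---|---|
| 0.4 | any | 0 | 0.40 |
| 0.4 | 0 | 5 | 11.2 / 33 = 0.34 |
| 0.4 | 0 | 10 | 11.2 / 38 = 0.29 |
| 0.4 | 0.2 | 10 | 13.2 / 38 = 0.35 |
| 0.4 | −0.2 | 10 | 9.2 / 38 = 0.24 |
| 0.3 | 0 | 10 | 8.4 / 38 = 0.22 |
| 0.5 | 0 | 10 | 14.0 / 38 = 0.37 |

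If the stoppers change as much as the finishers, there is no bias.

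**Illustration for satisfaction (assumed responses).** With 23 of 28 finishers satisfied, 23 / 28 = 82%, which meets the 80% criterion. If 5 more were reached and none was satisfied, 23 / 33 = 70%. With 10 more and none satisfied, 23 / 38 = 61%. With 10 more and all satisfied, 33 / 38 = 87%.

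**The case against.** The strongest reply is that the plan nowhere makes assessment conditional on finishing. Study Interventions says the outcomes are collected at all three time points. The compensation text pays for each of three assessments with no attendance condition, and offers every participant an exit interview. The analysis is intent-to-treat on all available data. A reader might infer that the plan excludes patients who stop, or that its intent-to-treat analysis is impossible. The text supports neither. The gap is an undefined date, not an exclusion. But intent alone does not tell a coordinator when to send a packet.

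Other strong readings also go too far:
- **About 10 patients will have no outcome.** The 26% covers all causes, so this is an upper bound.
- **The interval runs from 8 to 12 weeks, a 50% difference.** The first figure is a nominal schedule and the second an expected overall length. Neither is a range across patients, and the 12 weeks might even include the 1-month follow-up (8 + 4.35 = 12.35).
- **The sickest are assessed latest.** This is plausible, but no section says so.
- **All assessments should be re-dated from baseline.** Anchoring to the end of treatment is a legitimate choice for a pre-to-post pilot. PROMIS asks about the past 7 days, so a week-12 date would leave an 8-week finisher without the planned immediate measure and place it near that patient's planned follow-up.

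It is also fair that weeks-since-baseline coding partly deals with unequal intervals, and that with no control arm, disease course is mixed into the change under any schedule.

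**Conclusion.** The point holds in a limited form. Both post-baseline assessments are defined only relative to the end of the intervention, and patients who stop or stall have no due date. Following the text literally yields outcome and satisfaction data mainly from finishers, which undercuts the stated intent-to-treat analysis.

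The number of patients whose data could be recovered is unknown, between 0 and about 10 of 38. The direction of bias rests on the assumption that those who stop do less well or are less satisfied. The Background makes that plausible, but nothing in the plan establishes it. The effect sizes and percentages worked above are illustrations, not predictions.

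The change is worth making before data collection ends, because an outcome not collected cannot be restored in the analysis, and the result informs whether a larger trial goes ahead.

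**What to change.** - Keep both present time points for patients who finish the sessions.
- For every other enrolled patient who has not withdrawn consent, send the REDCap link or paper packet, including the CSQ, on a fixed backstop date counted from baseline, and again 1 month later, whatever the number of sessions attended. Week 12 is an example, in line with the expected intervention length. State a window.
- Say what the 12 weeks covers. If it includes the follow-up month, the backstop should be earlier. With week 12, the second packet falls at about week 16.3, close to the 4-month expected-survival criterion (4 × 4.35 = 17.4 weeks).
- Record the sessions attended by each assessment. Report the actual baseline-to-post interval beside the paired t-tests and Cohen's d.

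The cost is protocol wording, some scheduling and extra follow-up contact. Remote or paper completion is already planned, and the $40 per assessment already applies to all pilot participants (at most about 10 × 2 × $40 = $800 for those concerned). Session number and content do not change. The downside is that some stalled patients will be assessed before their last session. The session count allows those scores to be identified.
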